6.6 Study Variables and Their Measurement

6.6.1 Immunogenicity Variables

- 1. Cellular Immune Response to HIV-1 Antigens
 - a. Cells for the assessment of lymphocyte proliferation to HIV gp160 MN and gag IIIB protein will be collected on days 0, 14, 28, 42, 60, 104, 120, 194, 264, and 354.
 - b. Cells for the assessment of CTL activity and ELISPOT assay for interferon-g will be collected days 0, 14, 28, 42, 60, 104, 120, 194, 264, and 354.
 - c. Cells for the enumeration and identification of antigen specific interferon-g production using flow cytometry will be collected on Day -10, 28, 120, 194, 264 and 354.
- 2. Humoral immune responses to HIV

a. Antibody responses to homologous HIV-1 MN, gp120, and p24III-B and other non-hologous HIV-1 env antigens and peptides will be evaluated using plasma collected on days 0, 28, 60, 120, 194, 264, and 354.

b. Neutralizing antibody to HIV-1 MN strain, selected primary isolates, and other TCLA strains will be performed by the Immunology Laboratory at WRAIR, Rockville, MD.

3. Ancillary Studies

Human specimens collected under this protocol may be used to address other relevant questions regarding HIV-1 immunity if cells are available and CTL or neutralizations are elicited. Specifically, cells may be used to compare pre- and post-immune responses, compare assay methods of determination of cytotoxicity, characterize cytokine production, detect evidence of intracellular vaccine or cellular activation as a result of exposure to vaccine, or check for expression of vaccine components on the surface of autologous DC exposed to vCP205. Additionally, peripheral blood cells will be studied for evidence of sensitization to the vaccine (anti-ALVAC antibodies) and for evidence of primary cellular and humoral immunity against the test antigen KLH. Most methods described herein are standard immunologic techniques, however should new techniques become available to delineate HIV-1 immunity, these may be used as well. Aventis Pasteur, the US Army Medical Research and Material Command, and Rockefeller University will be informed of and consulted regarding these ancillary studies. These results will be discussed by the aforementioned parties prior to public disclosure.

6.6.1.1 Specimen Handling and Processing

- 1. Venipuncture will be done according to institutional guidelines.
- 2. Samples will be collected in the appropriate tubes as outlined in the attached table; substitution of tube types may be made as long as these are appropriate and do not interfere with the performance of the studies in question.
- 3. All biological samples to be analyzed by the clinical laboratory will be collected and processed according to institutional guidelines.
- All samples sent to the Specimen Processing Center will be labeled with the following information:
 Study number
 Subject number:
 Study day:
 Date
 Type of sample (serum, plasma, blood etc)

8901 Samples that will be analyzed after freezing should be prepared, labeled, and stored at the appropriate temperature. Specimens that are shipped will be correctly prepared, labeled, and kept at the correct temperature; all necessary shipping licenses/permits will be obtained.

6.6.1.2 Sample collection

Laboratory study	Type	Storage	Tube*	Amount
Hematology	blood	fresh	EDTA	3 ml
Chemistry	serum	fresh	red	3 ml
HIV Western blot	serum	fresh/frozen	red	1 ml

Serology	serum	fresh/frozen	red	1 ml
gp120/41 antibody	ser/plas	frozen	heparin	10 ml
Lymphocyte proliferation	blood	fresh/frozen	heparin	10 ml/8 ml
Cytotoxicity assay	blood	fresh/frozen	heparin	10 ml/8 ml

*Equivalent, appropriate substitutions to tube types are allowed

6.6.2 Safety Variables

6.6.2.1 Post-immunization Events Monitored as Possible Reactions to Vaccine

Selected local and systemic adverse events are routinely monitored in vaccine clinical trials as indicators of vaccine reactogenicity. It is recognized that each of these events, and particularly those of a systemic nature, may under some circumstances, in any individual subject, have a cause that is unrelated to study vaccines. However, as a matter of convenience and in accordance with common clinical practice, all such events occurring within 7 days of immunization (including the day of immunization) are herein termed "*post-immunization reactions*".

Post-immunization Reactions Occurring Immediately After Immunization

Following each vaccine administration, subjects will be observed in the clinic for 60 minutes. Study personnel will then evaluate the subject for any signs or symptoms of local or systemic reactions. These will be noted in the case report form. Possible local reactions that should be recorded include erythema and induration (measured using the ruler indicated on the diary card that will subsequently be provided to the subject), and pain/tenderness, or warmth at the injection site. Specific symptoms to be noted include fever (described in Toxicity Grading Scale, p. 64), fatigue, headache, myalgia, arthralgia, chills, nausea/vomiting, shortness of breath, chest pains, itching and rashes. For each immunization, oral temperature will be recorded prior to immunization and 60 minutes after immunization.

Local Reactions Within 7 Days Post-immunization (Study Days 0 to 6)

The subject will be asked to note occurrences of erythema and inducation (measured using the ruler included on the diary card), and pain/tenderness, or warmth at the injection sites daily for 7 days. These occurrences should be recorded on the diary card provided to serve as a reminder to the subject for the next clinic visit. A copy of the diary card will be kept by the study site.

Systemic Reactions Within 7 Days Post-immunization (Study Days 0 to 6)

The subject will also be asked to note occurrences of fever (> 38° C), fatigue, headache, myalgia, arthralgia, chills, nausea/vomiting, itching and rashes daily for 7 days and record these occurrences on the diary card mentioned previously. Oral temperature should be recorded by the subject 6 hours after immunization, and then daily for the next 7 days (for a total of 7 days of observation). If a medication is taken for treatment of fever, the temperature should be retaken and recorded 4 hours after the antipyretic dose to see if further treatment is necessary.

Post-immunization Contact

Between 24 and 48 hours after each immunization, the subject will be contacted by the investigator, study nurse, or research assistant to obtain local and systemic reaction data and to determine the subject's clinical status.

Instructions to Subjects Regarding Unusual or Severe Signs or Symptoms

Subject will be instructed to call the specified study personnel immediately if any unusual or severe sign or symptom appears after immunization. These subjects should be seen in the clinic at the time of maximal symptoms, if possible, and will be followed up clinically until resolution of symptoms.

6.6.2.2 Stopping Criteria

A severe adverse event or grade III/IV toxicity which is probably or definitely related to vaccination will result in discontinuation of vaccination for the individual. The volunteer will be asked to continue the follow-up schedule for the duration of the study.

Two severe adverse events or grade III/IV toxicity which are probably or definitely related to vaccination will result in discontinuation of the study arm. The volunteers will be asked to continue the follow-up schedule for the duration of the study.

Discontinuation of a study arm will prompt an immediate analysis of study safety data for all arms, a review of available immunogenicity data and consideration of modifying the design of the discontinued study arm (i.e.dose reduction) to minimize the risks to participants in the modified arm. New volunteers would be recruited for the modified study arm.

6.6.2.3 Other Adverse Events

An adverse event is any undesired, noxious or pathological change in a patient or subject as indicated by physical signs, symptoms, and/or laboratory changes that occurs following administration of one of the vaccines, whether or not considered vaccine related. This definition includes intercurrent illnesses or injuries, and exacerbation of pre-existing conditions. The following information will be included in IND adverse event reports: Subject identification number and initials; investigator's name and name of MTF; subject's date of birth, gender, and ethnicity; test article and dates of administration; signs/symptoms and severity; date of onset; date of resolution or death; relationship to the study drug; action taken; concomitant medication(s) including dose, route, and duration of treatment; date of last dose; and HSSRB protocol Log No A-9906.

Local reactions to immunization and selected systemic events will be solicited via subject interview and will be recorded on the post-injection reaction form. Reactions occurring within 7 days postimmunization will be recorded on a reactogenicity form. All other adverse events will be recorded on the adverse event form. All adverse events occurring up to 30 days after the fourth injections will be collected. After that, i.e., after visit 12 at week 37, only adverse events that are serious and/or necessitate a physician's visit or a prescribed medication will be collected. The subject should be followed carefully until the condition is resolved and/or the cause is identified. Any medication or other therapeutic measure taken to relieve symptoms of the medical problem must be recorded on the appropriate case report form page(s) in addition to the outcome of the adverse event.

Where a diagnosis is possible, it is preferable to report this rather than a series of terms relating to the diagnosis. When reporting a syndrome, indicate the associated signs and symptoms parenthetically following the syndrome rather than as separate events.

The *severity of events* reported on the adverse event form will be determined by the investigator, based on the Toxicity Grading Scale (Appendix 17.6) or if the event is not listed the event will be graded following these guidelines:

Mild (Grade 1):	Transient or mild discomfort. No limitation in normal daily activity.
Moderate (Grade 2):	Some limitation in normal daily activity.
Severe (Grade 3):	Unable to perform normal daily activity.
Serious (Grade 4):	Life threatening
Death (Grade 5):	

The *relationship of immunization* to adverse event (AE) will also be determined by the investigator, based on the following definitions:

Not Related:

AE obviously explained by another cause; OR The time of occurrence of AE is not reasonably related to vaccination.

Remotely Related:

AE more likely explained by causes other than vaccination.

Possibly Related:

Vaccine administration and AE occurrence reasonably related in time; AND AE explained equally well by causes other than vaccination.

Probably Related:

Vaccine administration and AE occurrence reasonably related in time; AND AE more likely explained by vaccination than by other mechanisms.

Definitely Related:

Vaccine administration and AE occurrence reasonably related in time; AND Vaccination most likely explains the AE; AND AE is consistent with pattern of vaccine-related events.

The definition of a serious adverse event is as follows:

A serious adverse event is defined as any untoward medical occurrence that:

-Results in death.

-Is life threatening (i.e., the patient was, in the opinion of the Investigator, at immediate risk of death from the event as it occurred).

-Requires or prolongs inpatient hospitalization (elective hospitalization excluded).

-Results in persistent or significant disability/incapacity, (i.e., the event causes a substantial disruption of a person's ability to conduct normal life functions).

-Is congenital anomaly/birth defect of a pregnancy arising while on study

-Is an important and significant medical event that, based upon appropriate medical judgment, may jeopardize the patient or subject and may require medical or surgical intervention to prevent one of the other outcomes defining serious. Written follow up information will be provided, when available, for all serious and unexpected adverse events in addition to the initial reports.

All unexpected adverse events (AE) will be reported to the WRAIR HURC and the HSRRB within 7 days. All deaths and any other serious adverse event will be reported to the FDA and the WRAIR

HURC and the HSRRB within 24 hours regardless of the perceived relationship with the vaccine. All other AE and SAE will be reported in accordance with all applicable regulations. Reports are made by telephoning the Secretary of the IRB and one of the following:

[name], DTMH Dept of Vaccine Research WRAIR [name] Rockville, MD 20850 w [contact] [contact] h [contact] [name] Chief Regulatory Affairs Henry M. Jackson Foundation [name] w [contact] [contact] h [contact]

Telephonic reporting must be followed by a written report within 24 hours to the IRB and to the following study investigators/team members:

[name], DTMH	[name]
WRAIR	Henry M. Jackson Foundation
[name]	[name]	Rockville, MD 20850
w [contact]	w [contact]
[contact]	[contact]
h [contact]	h [contact]
[name]	[name]
U.S. Military HIV Research Program	Aventis Pasteur
[name]	[name]
Rockville, MD 20850	Swiftwater, PA. 18370
w [contact]	USA
[contact]	[contact]
h [contact]	[contact]

Further immunizations should not be given to any subjects who have experienced a serious adverse event, whether related to vaccine or not, until written approval is obtained from the Principal Investigator or their designee.

6.6.2.4 Diagnostic Algorithm to Differentiate Immunogenicity from HIV Infection:

Diagnostic HIV testing will be carried out using an algorithm as described below. Information to the clinical staff at the vaccine trial site will not include the results of specific tests, but will rather state only "infected" or "not infected". This system will allow timely HIV testing without compromising the double-blind nature of the trial.

An FDA-approved HIV-1 ELISA assay will be performed five times throughout the course of the protocol (days -90 to -30, 0, 90, 194, and 354). If the ELISA is reactive, an FDA-approved HIV Western blot will be performed. If the Western blot is positive, HIV molecular diagnostics (Roche Amplicor) will be performed.

If the molecular diagnostics assay is positive, the person is suspected of being HIV positive and called back within 2 weeks for repeat testing. A verification blood specimen is obtained for HIV RNA. If repeat Amplicor tests are positive (both positive), then the person is considered HIV positive. If repeat tests are discordant, the person is called back and repeat testing is done until a definitive diagnosis is made (either the person is uninfected or infected).

6.6.2.5 Management of Volunteers with HIV-1 Infection During the Trial

- 1. If a volunteer is found to be HIV-infected during the trial, he/she will be excluded from further immunizations in the trial.
- 2. All vaccine recipients will also be offered diagnostic HIV testing and counseling 12 and 18 months after the last immunization (See HIV Testing Algorithm, Section 6.6.2.4).
- 3. Trial participants who are found to be infected with HIV-1 during the trial will be referred to a local physician and a designated clinic that specializes in long-term HIV care and treatment.
- 4. The staff of the designated clinic will be provided with the test results upon which the diagnosis of HIV infection is based. The clinic will also be provided with CD4 T cell count and HIV viral RNA quantitation (viral load).
- 5. Any trial participant who received vaccine and becomes HIV infected during the period of immunization, and up to 18 months post last immunization, will be offered enrollment, if eligible, in a protocol studying the natural history of HIV infection.

6.7 Procedural Flow Chart

6.8 Volunteer's Vaccine Schedule

6.9 Statistical Methods and Determination of Sample Size

6.9.1 Statistical Plan: Design and Sample Size Calculation

The data will be analyzed by DCAC. Any data analyses carried out independently by investigators should be submitted to WRAIR before publication or presentation.

The trial as designed has 3 groups:

Group I: Subcutaneous reinjection of *ex vivo* generated vCP205 transfected autologous dendritic cells Groups II and III: Intradermal or intramuscular injection of vCP205

The primary safety measurements include data from the clinical laboratory tests, observed immunization reactions (local and systemic) and adverse events. The primary immunogenicity data focus on cellular responses which will be assayed by both blastogenesis (lymphocyte proliferation) and cell mediated cytotoxicity.

This study is intended as a proof-of-concept to test the safety of the dendritic cell and ID delivery routes. It is not a definitive hypothesis testing study aimed at evaluating the relative immunogenicities (as measured by CTL response) of the IM, ID and DC arms. Despite this, we were able to determine the power with which differences between the DC arm and the better of the IM or ID arms could be detected. Assuming 100% (8 of 8) CTL response in the DC arm and 38% (3 of 8) response in the IM or ID arm, we would have approximately 70% power to detect a true difference in CTL response between the two arms if one actually exists. Additional information provided by immunomonitoring using ELISPOTs and intracellular flow cytometry (for IFN-gamma production) and blastogenesis assays (lymphocyte proliferation), we believe, will allow the study to determine if DC or ID routes are substantially better than the IM route.

All subjects receiving at least one injection of vaccine will be included in the safety and tolerability analyses. All data exclusions, including premature terminations, will be detailed and tabulated according to vaccine group. Data listings will include all subjects.

Demographic data obtained during the baseline visit will be listed for each subject. Summary statistics will be tabulated for each vaccine group. Subjects will be assessed for comparability at baseline. Descriptive statistics will be presented for continuous variables (age, height, weight). Frequency counts and percents will be presented for categorical variables (age, sex, and race).

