The non-adherent cells are washed away and the remaining cells (enriched monocyte fraction) are treated with clinical grade recombinant human Granulocyte Monocyte-Colony Stimulating Factor (rHuGM-CSF) and recombinant human Interleukin-4 (rHuIL-4) for 5 days. These cells are then harvested from the wells and re-plated into another plastic dish and treated with autologous monocyte conditioned medium (MCM). This MCM will be generated from the donor early in the study (from initial leukopheresis) and is used to mature the DC as a means of increasing the immunostimulatory capacity of the cells and in stabilizing their phenotype.

One of the main goals of this study is to transfect the DCs with a canarypox expressing HIV immunogens and test their capacity to induce an immune response following subcutaneous administration. Specifically, we hope to see a robust increase in the cellular immune response to the vaccine delivered via dendritic cells when compared to the standard intramuscular route. Intradermal delivery may be a more straightforward way to efficiently target the DC *in vivo* and thereby avoid *ex vivo* manipulation. Several existing vaccines are specifically designed to be given intradermally (rabies, cholera, and hepatitis B) for maximal humoral immunogenicity ³¹⁻³³. Other pox vaccines delivered intradermally have induced broader immune responses when compared to intramuscular delivery ³⁴. Skin dwelling DCs reside mainly in the epidermis and dermis and the ID injection of the vaccine may enhance its delivery to the local DC system. If the ID route facilitates vaccine access to the skin DCs, we would expect an improvement in immune response rate (~30-50%) to the standard IM route. Therefore, we expect to see the typical modest cellular response rate (~30-50%) to the standard IM route ⁵⁴⁻⁶¹, an improved response to the intradermal delivery route, and the maximal immune response to the directly targeted (*ex vivo*) pulsed DC.

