This study will provide new, preliminary data regarding the respective immunogenicities of intradermal and *ex vivo* DC immunization with vCP205 relative to the moderately immunogenic IM route in normal human volunteers. The study is not designed to resolve the null hypothesis.

			Months			
Group	Vaccine/	Subcutaneous	0	1	3	6
	Placebo*	Route				
Ι	8/4	DC	DC-vCP205 KLH pulsed or KLH pulsed DC only	DC-vCP205 or DC only	DC-vCP205 or DC only	DC-vCP205 or DC only

Subcutaneous Administration of vCP205 via transfected, autologous dendritic cells

Vaccine = vCP205 transfected DC pulsed with KLH, *Placebo = DC pulsed with KLH only (control DC) delivered in 2 x 0.2 ml subcutaneous injections. The KLH is used in the first vaccination only. $vCP205 = \sim 10^{6.5} \text{ TCID}_{50} (1 \text{ vial})$ reconstituted in1 ml sterile water/ 2-3 x 10^{6} DC

Intradermal or Intramuscular Administration of vCP205 via injection

			Months			
Group	Vaccine/ Placebo ¹	Route	0	1	3	6

II	8/4	Intradermal	vCP205	vCP205	vCP205	vCP205
III	8/4	Intramuscular	vCP205	vCP205	vCP205	vCP205

 $ID = \sim 10^{6.5} TCID_{50} (1 \text{ vial})$ reconstituted in 1 ml sterile water, delivered in 4 x 0.125 ml intradermal injections (0.5 ml total dose).

 $IM = \sim 10^{6.5} TCID_{50}$ (1 vial) reconstituted in 1 ml sterile water, delivered in a single 1 ml intramuscular injection (1.0 ml total dose).

 1 Placebo = sterile saline

6.2 Rationale for the Study Arms:

Group I. Delivery of ALVAC-HIV vCP205 to autologous *ex vivo* generated DC. We will directly target the dendritic cell as a means of maximizing the antigen presentation of encoded HIV-1 genes within the vaccine vector. Theoretically, this arm would serve as the optimal antigen delivery method in this descriptive study. It will provide important conceptual information on the benefits of directly loading critical antigen presenting cells with vectors for HIV vaccine development. If the results indicate beneficial effects of directly targeted-DC, this type of study will lay the groundwork for future vaccine development with an emphasis on *in vivo* DC targeting. We will include the use of KLH as a control antigen in this arm (for the first injection only) as means of quality control to ensure that the canarypox transfection process is not inhibitory for DC function in some way. We can then reasonably use the anti-KLH (primary) immunity that would develop in the control DCs as an internal referent for this arm.

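### The stated power of about 70% for CTL response is not reproduced by either named test, and it is calculated for a different comparator from the one announced

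*Protocol*

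**What the plan says.** Section 6.9.1 says that the study is not meant as a definitive test of relative immunogenicity. It then says that the sponsor could nevertheless determine "the power with which differences between the DC arm and the better of the IM or ID arms could be detected". The inputs are "Assuming 100% (8 of 8) CTL response in the DC arm and 38% (3 of 8) response in the IM or ID arm", and the result is "we would have approximately 70% power to detect a true difference in CTL response between the two arms if one actually exists". That paragraph names no test and no significance level. Section 6.9.3 supplies them for the trial as a whole: chi-square and Fisher's exact tests, two-sided at 0.05, with no rule for choosing between the two.

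The paragraph closes with the sponsor's belief that the ELISPOT, flow cytometry and proliferation data "will allow the study to determine if DC or ID routes are substantially better than the IM route". Section 6.1 says: "The study is not designed to resolve the null hypothesis". Section 4 puts the usual response to the IM route at about 30 to 50% and expects "an improved response to the intradermal delivery route, and the maximal immune response to the directly targeted" DC arm.

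**The concern.** This is the only power statement in the protocol, so a reader will take it as the support for 8 vaccinees per arm. Three things look wrong.

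- **The figure.** With 8 per arm and a DC rate of exactly 100%, power can be enumerated by hand, and 70% does not come out for either named test.
- **The comparator.** The paragraph announces the better of two arms and then works with one fixed 3/8 rate and a two-arm comparison. Beating the better of two arms is harder than beating one arm named in advance.
- **The closing claim.** It promises that the study will settle whether DC or ID is substantially better than IM, which Section 6.1 disclaims. A non-significant ID result could then be read as evidence of no benefit.

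**Working it through.** **Inputs.** Vaccinees: 8 per arm (Protocol Summary; Section 6.5.3). DC rate 100%; comparator rate 3/8 = 37.5%, printed as 38% (Section 6.9.1), so both values are run. Tests and level: chi-square and Fisher's exact, two-sided 0.05 (Section 6.9.3).

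**Formula.** With a true DC rate of 100%, the DC arm always shows 8/8. Power is therefore P(X ≤ c), where X ~ Binomial(8, p) is the comparator count and c is the largest count that still gives p ≤ 0.05 against 8/8.

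**Finding c.**

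| Comparator | Fisher p | Yates chi-square p | Uncorrected chi-square p |
|---|---|---|---|
| 3/8 | 2 × 56/4368 = 0.0256 | 0.031 | 0.007 |
| 4/8 | 2 × 70/1820 = 0.0769 | 0.083 | 0.021 |
| 5/8 | 0.200 | 0.200 | 0.055 |

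So c = 3 for Fisher and Yates, and c = 4 for the uncorrected chi-square.

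**The plan's own case: DC against one arm.**

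- Fisher or Yates, p = 0.375: 0.0233 + 0.1118 + 0.2347 + 0.2816 = 0.651. At p = 0.38 it is 0.640.
- Uncorrected chi-square, p = 0.375: 0.651 + 0.211 = 0.863. At p = 0.38 it is 0.856.

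The stated 70% lies between the two. Of the approximations tried, only a noncentral-t formula with pooled binomial variance comes close (70.8% at 37.5%, 70.3% at 38%), and the protocol does not name it.

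**Does the 86% hold the stated level?** Enumerating all 8 by 8 tables with equal true rates, the uncorrected chi-square rejects 6.7% of the time when both rates are 37.5%, and up to 7.7% (both rates 50%). At 8/8 against 3/8 the expected number of non-responders is 5/2 = 2.5 per arm, which is small for that test.

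**Comparator taken as the better of two.** If the comparator is the arm with the higher observed count, DC is significant only when both arms have c or fewer responders. With independent arms, power is P(X₁ ≤ c) × P(X₂ ≤ c).

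- Both truly 37.5%: Fisher 0.651² = 0.424; uncorrected chi-square 0.863² = 0.744.
- Both truly 38%: Fisher 0.640² = 0.410; uncorrected chi-square 0.856² = 0.732.
- One arm at 38% and the other lower, Fisher: 51.6% (other arm 30%), 60.4% (20%), 64.0% (0%).

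With a better arm at 3/8, Fisher power is therefore between 41% and 65% on each of these readings.

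**Sensitivity and ID against IM, Fisher, comparator 37.5%.** These rates are assumptions, not protocol figures.

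- DC truly 90%: 44%.
- ID 62.5% against IM 37.5%: 9.5%.
- ID 75% against IM 37.5%: 21%.

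**The case against.** The strongest reply is that the document does not commit to Fisher's test. It names chi-square as well, and the uncorrected version gives 86% for one comparator and 73 to 74% for the better of two, a few points above the stated figure. This stands as far as it goes: a reader might infer that the protocol's own test shows 70% to be too high, but no single test is fixed. What weakens the reply is that the uncorrected test exceeds the 0.05 level that Section 6.9.3 sets, so its power is not power at that level.

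A reader might also infer that the true power is 42%. The document does not support that as a flat statement. The figure needs both arms to respond at 3/8, independence, and selection of the comparator by observed count. Section 6.9.1 gives one rate and speaks of two arms, which equally allows a fixed comparator at 64 to 65%.

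Third, the 10 to 21% for ID against IM does not refute the closing sentence. That sentence relies on additional, partly quantitative assays and is offered as a belief; a dichotomous CTL comparison at assumed ID rates does not measure what those assays could show. Its fault is the conflict with Section 6.1.

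Finally, the figure is worded as approximate, the study is declared not to be definitive hypothesis testing, and the protocol ties no decision rule to the 70%. This stands and limits the severity.

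**Conclusion.** The stated power is not reproduced for the comparison that it describes. At two-sided 0.05 with 8 per arm, Fisher's test gives 65% (37.5%) or 64% (38%), a shortfall of about 5 to 6 points. The uncorrected chi-square gives 86% but does not hold the level. The announced comparator and the calculated one also differ; under Fisher, with both arms truly at 3/8 and the higher observed arm as comparator, power falls to about 42%. All these figures assume a true DC rate of 100% and all 8 vaccinees analysed in each arm. Severity is moderate to minor: the trial is small and largely descriptive, but this is its only power statement and it should be right.

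**What to change.** In Section 6.9.1, name the test (Fisher's exact, two-sided 0.05) and one comparator: DC against IM, the arm that Section 5 already uses as the reference. Replace the power sentence with wording such as:

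> With 8 vaccinees per arm, power is about 65% for 100% against 37.5% (3/8), and about 44% if the DC rate is 90%. If the comparator is the better observed of IM and ID and both are truly 37.5%, power is about 42%.

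Keep the 37.5% label, because at 38% the first and last figures become 64% and 41%. Reword the closing sentence so that the additional assays describe the DC and ID routes relative to IM, in line with Section 6.1. If a figure for ID against IM is wanted, say that Fisher power on the CTL endpoint alone is about 10% (62.5% against 37.5%) to 21% (75% against 37.5%), with the ID rates marked as assumptions.

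The cost is wording only. Sample size and conduct are unchanged, and the stated power becomes less favourable.
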